**Reminder: Please have the completed diary on hand at each phone call or video contact follow up.**

Symptoms	Day 8		Day 9		Day 10		Day 11		Day 12		Day 13		Day 14	
	Yes	No	Yes	No	Yes	No	Yes	No	Yes	No	Yes	No	Yes	No
Recent cough or aggravation of chronic cough														
Fever (enter temperature)														
Feverish/chills (temperature not taken)														
Sore throat														
Runny nose														
Shortness of breath/difficulty breathing														
Nausea/vomiting														
Headache														
General weakness														
Pain (muscular, chest, abdominal, joint, etc.)														
Irritability/confusion														
Diarrhea														
Sudden Loss of smell (anosmia)														
Comment or other, specify:														

**Reminder: Please have the completed diary on hand at each phone call or video contact follow up.**

## Revision History

Version	Date (DD-MMM-YYYY)	Author	Summary of Changes
Final	29-APR-2021	[name]	Initial version

## LIST OF ABBREVIATIONS

ACE2	Angiotensin Converting Enzyme 2
AE	Adverse Event
eCRF	Electronic Case Report Form
CRF	Case Report Form
DSMB	Data and Safety Monitoring Board
EC	Ethics Committee
e-Consent	electronic Consent
ICF	Informed Consent Form
ICH	International Council for Harmonisation
ITT	Intent To Treat
IUD	Intrauterine device
IRB	Institutional Review Board
LPS	Lipopolysaccharides
MHICC	Montreal Health Innovations Coordinating Center
PCR	Polymerase Chain Reaction
qPCR	quantitative Polymerase Chain Reaction
PP	Per Protocol
PO (po)	Per os
PRN	pro re nata (as necessary)
SAE	Serious Adverse Event
SOPs	Standard operating procedures
SAP	Statistical Analysis Plan
SUSAR	Suspected Unexpected Serious Adverse Reaction
TESS	Treatment-Emergent Signs and Symptoms
WMA	World Medical Association

## 1 INTRODUCTION

The purpose of this statistical analysis plan (SAP) is to present the statistical methodology that will be used for the final analysis of Montreal Heart Institute protocol MHICC-2020-003. This plan also provides a description of the tables, figures and listings that will be included in the final statistical report. It is based on the protocol dated 17FEV2021 and on the annotated case report form (CRF) version 2.0. In case of differences in terms of descriptions or explanations between the SAP and the clinical protocol, the SAP will supersede the protocol. Any deviation to this SAP would be reported in the statistical report.

## 2 STUDY DESCRIPTION

### 2.1 Study Design

This will be a randomized, double-blind, placebo-controlled study. The study will include subjects from Quebec diagnosed with COVID-19 infections. Following informed consent, 216 subjects meeting all inclusion and no exclusion criteria will be randomized to receive either hesperidin (1000 mg q.d.) or placebo (1:1 allocation ratio) for 14 days. Investigational drug will be delivered to the patients' homes. In addition, patients will be provided with an oral electronic thermometer as well as a daily symptoms diary (see Appendix A). Follow-up phone assessments will occur after 3, 7, 10, and 14 days following randomization for evaluation of the occurrence of any trial endpoints or other adverse events. Electronic CRF (eCRF) will be completed by the research personnel over the phone with the patients.

The schedule of visits for this study is outlined in Appendix B. However, a patient may be evaluated at any time for safety concerns.

### 2.2 Study Objectives

The primary objective of the study is to determine the effect of hesperidin therapy on the presence of selected COVID-19 symptoms (fever, cough, shortness of breath or anosmia) at 3, 7, 10, and 14 days following randomization.

The secondary objectives are:

- 1- To determine the effect of hesperidin therapy on the mean number of COVID-19 symptoms at 3, 7, 10, and 14 days following randomization.
- 2- To determine the effect of hesperidin therapy on the duration of COVID-19 symptoms.
- 3- To determine the effect of hesperidin therapy on the presence of each individual COVID-19 symptoms at 3, 7, 10, and 14 days following randomization.

The exploratory objectives are:

- 1- To evaluate the effect of hesperidin therapy on the presence of each individual COVID-19 symptoms on a daily basis based on a patient symptoms' diary.
- 2- To evaluate the effect of hesperidin therapy on COVID-19-related hospitalization, mechanical ventilation and death in the 14 days following randomization.

### 3 Datasets Analyzed

Subjects who were not eligible for randomization but who have been erroneously randomized into the study will be excluded from all datasets analyzed, if they did not take study medication. In this study, pregnancy tests are shipped with the medication at randomization. In case of positive pregnancy test, women will not be eligible and will also be excluded from all datasets analyzed, if they did not take study medication.

#### 3.1 Intent-To-Treat (ITT) Population

All patients randomized that have been delivered study medications will be included in the ITT population (i.e. subjects having a randomization number on the Randomization Form of the electronic case report form (eCRF)), excluding randomized women whose pregnancy test is positive. In the ITT population, subjects allocated to a treatment group by randomization will be followed up, assessed and analyzed as members of that group irrespective of their compliance to the planned course of treatment. ITT population will be approved by the sponsor prior to database lock.

#### 3.2 Safety Population

All patients who took at least one dose of study medication will be included in the safety population. Patients will be assigned according to the true treatment received for analysis purposes. If a patient receives hesperidin at randomization or as supplemental bottle, the true treatment received will be imputed as hesperidin. The subjects of the safety population will be identified using the variable MEDIC of the Study Medication Administration Form of the eCRF. If a woman with a positive pregnancy test took at least one dose of study medication even it is not recommended, she will be included in the safety population. The same will apply if the unlikely case of a subject erroneously randomized who took at least one dose of study medication. Safety population will be approved by the sponsor prior to database lock.

### 4 EFFICACY ENDPOINTS

#### 4.1 Primary Efficacy Endpoint

The primary endpoint will be the proportion of subjects with any of the following COVID-19 symptoms: fever, cough, shortness of breath or anosmia, at day 3, 7, 10 and 14 of the patient's symptoms diary.

Presence of these symptoms (Yes/No) will be identified using the Covid-19 Symptoms Form of the eCRF (variables COUGH, FEVER [considered a symptom if greater than 38°], SBREATH and ANOS respectively) at DAY 3, DAY 7, DAY 10 and DAY 14.

#### 4.2 Secondary Efficacy Endpoints

- Mean number of COVID-19 symptoms (range 0 – 13) at day 3, 7, 10 and 14 of the patient symptoms' diary. This endpoint will be derived using the Covid-19 Symptoms Form of the eCRF at

DAY 3, DAY 7, DAY 10 and DAY 14. For each subject, the number of symptoms reported as 'Yes' will be calculated, adding one if the symptom "Fever" is greater than 38°.

- Duration of COVID-19 symptoms, defined as the number of days between randomization and complete disappearance of symptoms. More specifically, duration of COVID-19 symptoms will be taken as day of complete disappearance (because randomization is DAY 0). Subjects who will still have at least one symptom at their last assessment will be censored at the day of this last assessment.

To determine day of complete disappearance of symptoms, all symptom assessments from the patient's diary will be sorted by day (variable DAYPARM). At each time point, the assessment will be categorized as complete disappearance of symptoms (if number of symptoms = 0) or no complete disappearance of symptoms (if number of symptoms > 0).

- ✓ If there is complete disappearance of symptoms at Day 14 (or last assessment), day of complete disappearance is the first day when complete disappearance occurred with no relapse.
- ✓ If there is no complete disappearance of symptoms at Day 14 (or last assessment), the day of this last assessment will be the censoring day.

It should also be noted that subjects who do not complete the study will be classified as still having symptoms (i.e. no complete disappearance) REGARDLESS if symptoms disappeared earlier. Date of censoring will be the date of study discontinuation.

- For each of the 13 COVID-19 symptoms listed in the appendix, proportion of subjects with the symptom at day 3, 7, 10 and 14 of the patient symptoms' diary. Presence of these symptoms (Yes/No) will be identified using the Covid-19 Symptoms Form of the eCRF (variables COUGH, FEVER [considered a symptom if greater than 38°], FEVERISH, STHROAT, ..., ANOS) at DAY 3, DAY 7, DAY 10 and DAY 14.

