### **4.2 Patient Selection Criteria**

#### **4.2.1 Inclusion Criteria:**

All of these criteria must be met:

- Covid-19 positive by polymerase chain reaction (PCR) testing;
- Participant must be able to evaluate their symptoms and report them in the symptoms' diary;
- Patients must be able to take their oral temperature daily with an electronic thermometer provided to them with study materials;
- Males and females, at least 18 years of age, capable and willing to provide informed consent;
- Female patient is either not of childbearing potential, defined as postmenopausal for at least 1 year or surgically sterile, or is of childbearing potential and practicing at least one method of contraception and preferably two complementary forms of contraception including a barrier method (e.g. male or female condoms, spermicides, sponges, foams, jellies, diaphragm, intrauterine device (IUD)) throughout the study;
- Patient must have received a diagnosis of COVID-19 infection within the last 48 hours and have one or more symptoms;
- Outpatient setting (not currently hospitalized or under immediate consideration for hospitalization);
- Patient must be able and willing to comply with the requirements of this study protocol.

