## **5 STUDY METHODOLOGY**

### **5.1 Efficacy Outcomes**

- The **primary endpoint**:  
Proportion of subjects with any of the following COVID-19 symptoms: fever, cough, shortness of breath or anosmia, at day 3, 7, 10 and 14.
- The **secondary endpoints**:
  - 1- Mean number of COVID-19 symptoms (range 0 – 13) at day 3, 7, 10 and 14.
  - 2- Duration of COVID-19 symptoms, defined as the number of days between first symptoms and complete disappearance of any symptom.
  - 3- For each COVID-19 symptom listed in the appendix, proportion of subjects with the symptom at day 3, 7, 10 and 14.

Duration of symptoms will be determined as follows:

- If randomization and study product reception by participant occur the same day, first day of symptoms will be defined as the day of randomization;
- If randomization and study product reception by participant occur on different days, first day of symptoms will be defined as the day of study product reception.

- The **exploratory endpoints**:
  - 1- For each COVID-19 symptom listed in the appendix, proportion of subjects with the symptom on a daily basis based on patients' diary.
  - 2- Composite of COVID-19-related hospitalization, mechanic ventilation or death in the 14 days following randomization.

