## 8 APPENDICES

### APPENDIX A COVID-19\_ SYMPTOMS LOG

Symptoms	Day 1 Yes No	Day 2 Yes No	Day 3 Yes No	Day 4 Yes No	Day 5 Yes No	Day 6 Yes No	Day 7 Yes No
Recent cough or aggravation of chronic cough	 						
Fever (enter temperature)							
Feverish/chills (temperature not taken)	 						
Sore throat	 						
Runny nose	 						
Shortness of breath/difficulty breathing	 						
Nausea/vomiting	 						
Headache	 						
General weakness	 						
Pain (muscular, chest, abdominal, joint, etc.)	 						
Irritability/confusion	 						
Diarrhea	 						
Sudden Loss of smell (anosmia)	 						
Comment or other, specify:							

Reminder: Please have the completed diary on hand at each phone call or video contact follow up.

Symptoms	Day 8 Yes No	Day 9 Yes No	Day 10 Yes No	Day 11 Yes No	Day 12 Yes No	Day 13 Yes No	Day 14 Yes No
Recent cough or aggravation of chronic cough	 						
Fever (enter temperature)							
Feverish/chills (temperature not taken)	 						
Sore throat	 						
Runny nose	 						
Shortness of breath/difficulty breathing	 						
Nausea/vomiting	 						
Headache	 						
General weakness	 						
Pain (muscular, chest, abdominal, joint, etc.)	 						
Irritability/confusion	 						
Diarrhea	 						
Sudden Loss of smell (anosmia)	 						
Comment or other, specify:							

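### The symptom count gives fever two separate points through diary rows that are labelled as alternatives, and the carry-forward rule can mis-score even a diary completed as labelled

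*SAP*

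**What the plan says.** SAP 4.2 defines the first secondary endpoint as "Mean number of COVID-19 symptoms (range 0 – 13) at day 3, 7, 10 and 14". For each subject, the number of rows marked Yes "will be calculated, adding one if the symptom" Fever is above 38°. The third secondary endpoint in the same section treats FEVER and FEVERISH as two of 13 separate items: "For each of the 13 COVID-19 symptoms listed in the appendix, proportion of subjects with the symptom at day 3, 7, 10 and 14".

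The log in SAP Appendix A, which has the same rows as the diary in Protocol Appendix E, contains these two entries:

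- "Fever (enter temperature": a temperature is written in, and there is no Yes/No box.
- "Feverish/chills (temperature not taken": a Yes/No box.

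Protocol 4.2.1 expects a reading every day: "Patients must be able to take their oral temperature daily with an electronic thermometer provided to them with study materials".

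SAP 6.2.1 adds two imputation rules. If only some of the 13 items are missing or not done on a day, each missing item takes its last observed value. If all items are missing on a day before a patient's death, every item is set to present, including fever above 38°.

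Neither document says how the two fever rows are to be scored together.

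**The concern.** By its label, the second fever row is for days on which the first is empty. The scoring rule ignores this and gives each row its own point. Fever can therefore weigh 1 or 2 in the total, depending on how a patient reads a label. The top of the stated range is also one point above what entries made as labelled can produce.

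The carry-forward rule adds a second problem. On a day completed as labelled, one of the two rows does not apply and may well be left blank. SAP 6.2.1 then treats the blank as missing and fills it from an earlier day, although the other row already answers the question. This reaches the total count and, in one pattern, the duration endpoint, because that endpoint requires a count of exactly 0.

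**Working it through.** **Inputs.** The 13 rows of SAP Appendix A: 12 Yes/No rows (one of them Feverish/chills) and one temperature row. The scoring rule of SAP 4.2. The imputation rules of SAP 6.2.1.

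**1. The plan's own figure.** 12 Yes/No rows + 1 for a temperature above 38° = 13. The stated range of 0 to 13 is the row count.

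**2. The range with the labels applied.** Setting the two fever rows aside leaves 13 − 2 = 11 rows. If at most one fever row can be positive on a day, the maximum is 11 + 1 = 12. Enumeration agrees: of 2^13 = 8192 patterns, 2^11 = 2048 have both fever rows positive. The remaining 6144 have a maximum of 12.

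**3. Same fever, different score.** Take a patient whose only finding is 38.5°.

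- Feverish/chills not ticked: 0 + 1 = 1.
- Feverish/chills ticked as well: 1 + 1 = 2.

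**4. Carry-forward, double count.** In both days below, the other 11 rows are Yes.

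| Day | Temperature | Feverish/chills | Score from entries | Score after SAP 6.2.1 |
|---|---|---|---|---|
| 6 | 38.5° | No | 11 + 1 = 12 | 12 |
| 7 | not taken | Yes | 11 + 1 = 12 | 11 + 1 + 1 = 13 |

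Both days were completed as labelled. The extra point on Day 7 comes from the imputed 38.5°.

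**5. Carry-forward, delayed recovery.** In both days below, the other 11 rows are No.

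| Day | Temperature | Feverish/chills | Score from entries | Score after SAP 6.2.1 |
|---|---|---|---|---|
| 6 | not taken | Yes | 1 | 1 |
| 7 | 36.8° | left blank | 0 | 0 + 1 = 1 |

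The Day 6 Yes is carried onto a day with a normal reading, so Day 7 does not count as free of symptoms. If the row stays blank on every later day, the Yes is carried to the last assessment. The patient is then censored instead of counted as recovered.

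**6. Imputation before death.** Setting every item to present gives 13.

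**7. Effect on the mean and on the comparison.** For double entries, the mean count in an arm rises by the share of its patients with both entries on that day. Let f be the share of an arm with a reading above 38°, and r the share of those patients who also tick Feverish/chills. Assume r is the same in both arms, as randomisation and blinding support in expectation.

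- Excess in an arm's mean = f × r.
- Addition to the between-arm difference = r × (f in one arm − f in the other).
- No treatment effect on fever: r × 0 = 0.
- An assumed true 10-point difference in fever, with r anywhere from 0 to 1: an addition of 0 to 0.10 symptoms, in the direction of the true difference.

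The documents give neither f at the assessment days nor r.

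**The case against.** The strongest reply is that the row covers chills as well as feeling feverish. Protocol 1.3 lists chills among the other symptoms, apart from fever, and the diary has no other row for them. SAP 4.2 names FEVER and FEVERISH as separate variables, so scoring them separately looks deliberate. A patient with 38.5° and chills may be reporting two things. This stands as a reading of intent, but then the parenthesis in the label is what conflicts with the count. Either way the SAP needs a rule for the pair.

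A second reply is that a patient who follows the label is never double counted on observed entries, and that research staff complete the eCRF by phone and may catch conflicts. The first part is right for observed entries, but it does not cover the carry-forward cases in steps 4 and 5. The second part cannot be checked, because the annotated CRF that the SAP cites is not among the documents.

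Three stronger readings are tempting and are not supported:

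- A reader might infer that the treatment comparison is biased by diary habits. The trial is randomised and double-blind and one rule serves both arms, so habits balance in expectation. Any addition to the difference is extra weight on a true fever difference.
- A reader might infer that a score of 13 is impossible. It is reachable through imputation, as steps 4 and 6 show. The limit of 12 applies to observed entries made as labelled.
- A reader might put a figure on the inflation. Assuming 20% to 40% of patients above 38° at Day 3, with 25% to 100% of those also ticking the second row, gives 0.20 × 0.25 = 0.05 up to 0.40 × 1.00 = 0.40 symptoms per patient. Neither assumption has a source in the documents. The 44% to 91% in the Protocol 1.3 table is an overall frequency of fever, not the share above 38° on a given day.

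**Conclusion.** The point holds in a limited form. The count scores as two points a pair of rows that the form presents as alternatives, and no rule caps or reconciles them. Observed entries made as labelled reach 12 at most. The carry-forward rule can mis-score a correctly completed diary, by adding a second fever point or by holding a recovered patient above 0.

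The consequence is noise and extra weight on fever in the first secondary endpoint, at most one point per patient per day, with some possible delay in the duration endpoint. How often this happens depends on whether patients mark No or leave the inapplicable row blank, and on how many enter both, which the documents do not show. The conclusion rests on reading the label literally.

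The primary composite uses FEVER only, so it is not double counted, and the sample size does not depend on this endpoint. Scoring 2 instead of 1 does not itself alter duration, since neither is 0. This is a correction worth making, not a threat to the trial's main conclusion.

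**What to change.** **SAP 4.2, total count only.** Let the two rows contribute at most one point per day: one if the temperature is above 38° or Feverish/chills is Yes, otherwise none. State the range as 0 to 12.

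**SAP 6.2.1.** Carry neither fever row forward on a day when the other is answered. This section also feeds the primary composite, so say that the exception applies to the total count and to the duration endpoint derived from it. Otherwise FEVER would become missing in the composite on days without a reading.

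**Leave unchanged.** Keep FEVER above 38° as its own item in the primary composite and the individual-symptom analyses. Merging the rows there would lose measured fever, which Protocol 1.3 groups with the symptoms it regards as less subjective. Report FEVERISH separately, with a note that by its label it applies to days without a temperature. Keep both raw rows in the listing.

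**Cost.** One derived variable, a few sentences, and reprogramming of Tables 2.2.1 and 2.2.2. The SAP states that it prevails over the protocol, so the change can be made there. The range will differ by one from the protocol's 0 to 13, and chills alongside a measured fever will not be counted separately. A sensitivity analysis on the 13-item count covers both.

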## 6 STATISTICAL METHODOLOGY

### 6.1 Determination of Sample Size

Sample size is based on the proportion of subjects with any of the following COVID-19 symptoms: fever, cough, shortness of breath or anosmia at day 7 since this time point will be the primary focus. Using a two-sided 0.05 significance level, sample sizes of 91 in both groups (182 total) will achieve 80% power to detect an absolute between groups difference of 20% in the proportion of subjects with the above COVID-19 symptoms at day 7. This is assuming that the proportions of patients with the above COVID-19 symptoms at day 7 will be 50% in the placebo group and 30% in the active treatment group. Factoring in a 15% drop out rate, a total of 216 patients will be randomized in the study (108 per group).

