#### 6.2.1 Handling of Missing Data

Subjects will be asked to assess daily the presence (Yes/No) of 13 COVID-19 symptoms for a duration of 14 days. Most efficacy endpoints rely heavily on the assessment of these symptoms so a rule has to be defined in case the symptoms are reported as 'Not Done' or are missing.

At any given day (DAY 1 to DAY 14), if some symptoms among the 13 symptoms are reported as 'Not Done' or are missing, these symptoms will be imputed as the last observation carried forward.

On the other hand, if, at any given day, all symptoms are reported as 'Not Done' or are missing, the following will be done:

- If the subject has died, then all symptoms will be imputed as 'Yes' (and symptom "Fever" as greater than 38°) if that day is prior to date of death.

- Otherwise, the symptoms will not be imputed and the assessment on that day will be considered missing.

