## 6.3 Study Subjects

### 6.3.1 Subject Disposition

Number of subjects randomized, number of subjects who took at least one dose of study medication, number of randomized subjects completing the study and reasons for discontinuation will be summarized overall and by treatment group. A listing of subject disposition will be provided and will include subject ID, date of informed consent, date of randomization, randomized treatment group, result of the pregnancy test, day of first dose, day of last dose, completion (Yes/No), date of discontinuation and reason for discontinuation. Subject disposition will also be presented with a flow chart.

The number of days between the positive diagnosis for COVID-19 infection and the date of randomization will be summarized overall and by treatment group for the ITT population. The same will be done for the number of days between the first COVID-19 symptoms prior to randomization and the date of randomization. The first COVID-19 symptoms prior to randomization will also be displayed.

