#### 6.4.2 Secondary Analysis

- Number of COVID-19 symptoms (range 0 – 13) will be summarized using descriptive statistics at 3, 7, 10 and 14 days, overall and by treatment group.

Mean number of COVID-19 symptoms will be compared between treatment groups using a repeated measures analysis of variance (ANOVA) model with terms for treatment group (placebo, hesperidin), time (3, 7, 10 and 14 days) and treatment group x time interaction. Contrasts under this model will allow for the comparisons of the mean number of symptoms at each time point. Mean differences will be presented with 95% confidence intervals and p-values. If more appropriate given the distribution of the data, a Poisson regression model for repeated measures could be used.

- Number and proportion of subjects with complete disappearance of COVID-19 symptoms after randomization will be provided overall and by treatment group. In those subjects, duration of symptoms will be summarized using descriptive statistics.

Duration of COVID-19 symptoms will be compared between treatment groups using a log rank test and Kaplan-Meier curves will be presented.

- Individual COVID-19 symptoms over time (3, 7, 10 and 14 days) will be presented and analyzed as the primary endpoint, using the statistical approach described in section 6.4.1.

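### SAP 4.2 discards the recorded recoveries of every non-completer in the symptom-duration analysis, with no reason and no sensitivity analysis; this costs power and is not reliably conservative (secondary endpoint)

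*SAP*

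**What the plan says.** SAP 4.2 sorts the diary by day and sets a general rule: "If there is complete disappearance of symptoms at Day 14 (or last assessment), day of complete disappearance is the first day" of a symptom-free run with no later relapse. A subject with symptoms at the last assessment is censored on that day.

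It then makes an exception: "subjects who do not complete the study will be classified as still having symptoms (i.e. no complete disappearance) REGARDLESS if symptoms disappeared earlier". For these subjects, "Date of censoring will be the date of study discontinuation".

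SAP 6.4.2 applies the definition twice: "Duration of COVID-19 symptoms will be compared between treatment groups using a log rank test", with Kaplan-Meier curves, and "Number and proportion of subjects with complete disappearance of COVID-19 symptoms after randomization will be provided overall and by treatment group". The table list in SAP 7 has a single duration table (2.2.2). SAP 6.2.1 deals only with missing symptom entries. No passage explains the exception or plans a second analysis of duration.

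Protocol 8.3.1 censors subjects who still have symptoms at the end of the study and is silent on those who recovered and then left. SAP 1 says the SAP prevails over the protocol, so the exception will be applied. Protocol 5.3 asks withdrawn subjects for the Day 14 call. Protocol 5.4 and SAP 6.3.1 record completion (the listing holds "completion (Yes/No), date of discontinuation and reason for discontinuation") but do not say whether a withdrawn subject with a Day 14 result counts as a completer.

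**The concern.** Take a subject who is symptom-free from Day 5 and leaves on Day 12. The general rule gives a recovery on Day 5. The exception removes that event and keeps the subject at risk, as unrecovered, through Day 12.

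Ordinary censoring removes only what was not seen; this rule removes what was seen. A true worst case would keep the subject unrecovered to Day 14; this rule lets the subject leave the risk set at discontinuation. So the rule has no fixed direction. It lowers the apparent recovery rate in each arm according to how many recovered subjects that arm loses. If both arms lose equally, the cost is power. If not, the log-rank comparison is biased against the arm that loses more. The proportion with complete disappearance in SAP 6.4.2 also reads low.

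**Working it through.** **The plan's own figures.** SAP 6.1 gives 91 per group for 50% versus 30% at Day 7. With unpooled variance, (1.960 + 0.842)² × (0.25 + 0.21) / 0.20² = 90.3, so 91. Then 91 / 0.85 = 107.1, so 108 per arm and 216 in all. The plan says: "Factoring in a 15% drop out rate, a total of 216 patients will be randomized in the study". At 15%, 0.15 × 216 is about 32 non-completers. The documents give no power, event count or effect size for duration.

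**Assumptions, none of them in the documents.** Placebo symptom-free at Day 14: r = 50% or 65%. Recovery rate ratio 1.6, so active daily recovery is 1 − (1 − p)^1.6. Daily relapse 0, 5, 10 or 15%. Departure uniform on Days 1-13 and independent of recovery.

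**Events, no relapse, 15% loss in each arm.** Recovery by Day 14 is r in placebo and 1 − (1 − r)^1.6 in active: 50.0% and 67.0%, or 65.0% and 81.4%.

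- Under the SAP rule only completers can have events: 108 × 0.85 × (0.500 + 0.670) = 107.4, or 108 × 0.85 × (0.650 + 0.814) = 134.4.
- The chance that a leaver had already recovered is the mean of 1 − (1 − r)^(k·c/14) over c = 1 to 13, with k = 1 (placebo) or 1.6 (active): 0.281 and 0.400, or 0.385 and 0.523.
- Discarded recoveries: 108 × 0.15 × (0.281 + 0.400) = 11.0, or 108 × 0.15 × (0.385 + 0.523) = 14.7.

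So 11 of 118 or 15 of 149 recoveries are dropped. Simulation gives 107.5 vs 118.5 and 134.3 vs 149.0.

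**Kaplan-Meier, no relapse.** With loss d and S(t) = (1 − r)^(t/14), the daily event rate under the SAP rule is h(t) = (1 − d)[S(t−1) − S(t)] / {(1 − d)S(t−1) + d(14 − t)/13}, and estimated recovery is 1 − Π[1 − h(t)]. At d = 0.15 this gives 46.5% for a true 50% and 60.7% for a true 65%. With no treatment difference, d = 0.10 against 0.20 gives 47.7% against 45.2%, or 62.2% against 59.1%: a gap made by the rule alone.

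**Crude proportion.** 0.85 × 50% = 42.5% and 0.85 × 65% = 55.2%, at every relapse rate. With recoveries counted it is 46.7-48.7% and 61.0-64.0%.

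**Log-rank power, 15%/15%** (simulation, 108 per arm, 40,000 trials per setting; Monte Carlo error at most 0.25 points). SAP rule vs recoveries counted:

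| Daily relapse | True 50% | True 65% |
|---|---|---|
| 0% | 64.7 vs 72.1 | 72.5 vs 81.5 |
| 5% | 48.5 vs 56.1 | 43.1 vs 53.1 |
| 10% | 36.2 vs 42.4 | 25.8 vs 32.1 |
| 15% | 29.4 vs 34.4 | 19.7 vs 23.3 |

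The loss is 2-7 points at 10%/10% and 1-3 at 5%/5%. It is nil if only symptomatic subjects leave (69.7% and 79.8% under both rules). If all departures fall on Days 8-13 with no relapse it is larger: 62.9 vs 73.7 and 68.8 vs 83.2.

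A separate simulation with exponential recovery, rate ratio 1.5, no relapse and 15% loss in both arms agrees. It loses 4-13 points over placebo recovery of 30-75%, and 17-20 points if every departure follows recovery.

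**Type I error.** At 15%/15% the SAP rule gives 4.8-5.3%. At an assumed 10%/20% split, total rejection in percent (SAP rule / recoveries counted / counted only if the last two diary days are symptom-free):

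| Daily relapse | True 50% | True 65% |
|---|---|---|
| 0% | 6.7 / 4.9 / 5.0 | 8.4 / 5.0 / 5.1 |
| 5% | 6.7 / 5.2 / 5.1 | 7.8 / 5.2 / 5.0 |
| 10% | 6.4 / 5.6 / 5.2 | 6.8 / 5.8 / 5.3 |
| 15% | 5.8 / 5.9 / 5.3 | 6.3 / 6.9 / 5.8 |

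Under the SAP rule 4.4-7.7% goes against the arm losing more, where 2.5% is nominal.

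**The case against.** The strongest defence is relapse. The endpoint requires disappearance without relapse, and a subject who leaves early cannot be shown relapse-free to Day 14. Of the recoveries that the alternative would credit to non-completers, 24-25% would relapse by Day 14 at 5% daily relapse, 43-45% at 10% and 58-59% at 15%. At 10-15% relapse the two Kaplan-Meier estimates err by similar amounts in opposite directions: the SAP rule 2.0-2.9 points low, counting recoveries 1.6-2.4 points high. At 15% relapse with a 10%/20% split, counting recoveries has the slightly worse type I error, and 4.7-5.9% then favours the arm losing more. It can also be said that this is an explicit prespecified choice on an unpowered secondary endpoint, that 15% is a sample-size allowance rather than a forecast, that subjects who stop medication are encouraged to stay in follow-up, and that nothing in the documents predicts unequal loss.

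Much of this stands. Relapse is a plausible motive, neither analysis is best everywhere, and the bias between arms needs unequal loss. It does not rescue the rule. The general rule in SAP 4.2 already credits recovery at the last assessment to completers whose later days are equally unseen. Holding a subject with a recorded recovery at risk as symptomatic until departure is not a neutral way to allow for relapse. And the SAP neither states this motive nor tests how far the result depends on it.

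**Conclusion.** The concern holds and should be fixed. SAP 4.2 discards recorded recoveries for all non-completers, and the plan gives no reason and no sensitivity analysis.

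At the planning drop-out rate, with departure unrelated to recovery, the cost is 7-10 power points at 0-5% daily relapse and 4-6 at 10-15%. It is small with few non-completers and nil if only symptomatic subjects leave. The rule is not reliably conservative: with unequal loss, false rejections fall mostly against the arm losing more, so a heavier placebo loss would favour hesperidin.

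All sizes rest on assumed recovery, relapse and departure patterns; only the 15% comes from the documents. The day-7 primary analysis and its sample size are not touched, and non-completers' symptom-free days still enter the other symptom analyses.

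**What to change.** Amend SAP 4.2 and 6.4.2 as follows.

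- **Main analysis.** A subject symptom-free at the last available assessment, including any Day 14 call after withdrawal, is recovered on the first day of that symptom-free run. A subject with symptoms at the last assessment is censored on that day.
- **Deaths.** A subject who dies is never counted as recovered. This fits SAP 6.2.1, which treats symptoms as present on fully missing days before death.
- **Proportion recovered.** Use the same definition in SAP 6.4.2.
- **Completion.** State what completing the study means for this endpoint, in particular for a withdrawn subject who has a Day 14 result.
- **Sensitivity analysis.** Keep the current rule as the sensitivity analysis and report the two results together as a bracket.
- **Option, useful if relapse is expected.** Count a non-completer as recovered only if at least the last two diary days are symptom-free. In the simulations this keeps type I error at 5.0-5.8% under the 10%/20% split, below the SAP rule at every relapse rate. Kaplan-Meier error is at most 1.5 points, and power is at most 1.1 points below the plain version.

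The cost is SAP wording and one extra run on diary data already collected. The downside is that relapse after an early departure is unseen, which is why the two analyses should be read together.
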